7.1 Study Design

The study does not involve any interventional measurements, e.g., receiving posaconazole injection and/or tablet, laboratory test for IA diagnosis. Under this protocol, all patients accepted posaconazole injection and/or tablet previously in the course of routine clinical practice.

This is a multicenter observational study involving prospective (Planned: Oct 2023-Dec 2024) and retrospective (Planned: Mar 2022- Oct 2023) data collection from target hospitals using a case report form during the planned recruitment period (Oct 2023-Dec 2024).

Chinese adult IA patients (\geq 18 years old) who have been treated with posaconazole for at least 7 days in accordance with NMPA's approved product information are potential subjects for the study.

After inclusion/exclusion criteria check: (1) The patients who have continued posaconazole treatment for 7 to 42 days and have dead or alive status available through day 42 will be evaluated for primary objective. (2) The patients who have continued posaconazole as first line treatment for 42 to 84 days and have treatment response data available (success or failure at the end of treatment or at a maximum duration of 84 days) will be evaluated for secondary objectives. (3) The patients who have continued posaconazole as salvage treatment for 7 to 84 days and have treatment response data available (success or failure at the end of treatment response data available (success or failure at the end of treatment for 7 to 84 days) will be evaluated for secondary objectives. The demographic, clinical characteristics and treatment patterns will be described in this study.

Information will be collected by using a case report form during the planned recruitment period (Oct 2023-Dec 2024) including but not limited to outpatient or inpatient medical records, lab reports, prescription records, etc., by qualified investigators.

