PRODUCT: MK5592	PROTOCOL/AMENDMENT VERSION NO.: 2
REVOPS ID NO: NIS102646	CORE DRC APPROVAL DATE: 18-SEP-2024
EPIDEMIOLOGY NO.(PE STUDIES ONLY): EP08047.004	

multicenter observational study prospectively and retrospectively collecting effectiveness information in Chinese adult IA patients with posaconazole.

The advantage of the observational study is to conduct the study without any intervention, which will obtain information on patients receiving posaconazole to better reflect real-world clinical practice. Currently, there is no database in China that can be used directly to assess the effectiveness of posaconazole. This study using medical records from multicenter as the basic data source is the most feasible research methods.

According to the evaluation of the number of IA patients in the potential research sites, extensiveness of prophylactic use and the enrollment difficulty and speed in clinical trial, the observed number of IA patients with posaconazole treatment in this study might be limited, hence this study proposed a combination of prospective and retrospective study design.

6 **RESEACH QUESTION AND OBJECTIVES**

The aim of this study is to assess all-cause mortality of posaconazole injection and/or tablet treatment of IA in Chinese adult patients by an observational study involving prospective and retrospective data from target hospitals using a case report form during the planned recruitment period (Oct 2023-Dec 2024).

6.1 **Primary Objective**

1. To assess all-cause mortality at day 42 of IA (proven, probable, possible) in Chinese adult patients who receive at least 7 days² of posaconazole injection and/or tablet formulations.

 2 Considering the real-world medication adherence of patients, in this study, if the prescribed duration of medication is specified and the actual duration of medication reaches 80% or more of the specified duration, it can be included in the analysis.

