7.2 Setting

7.2.1 Study Population

The overall study population will consist of IA adult Chinese patients (proven, probable, possible⁵) who received at least 7 days of posaconazole (injection and/or tablet formulations) treatment (including monotherapy and combination⁶ therapy) from Mar 2022 to Dec 2024 (planned date of last patient in).

⁵ Follow the definition of 2020 EORTC/MSGERC or 2021 EORTC/MSGERC-ICU consensus criteria [Donnelly, J. P., et al 2020] (see Annex 5).

⁶Combination therapy is defined as patient use posaconazole (injection and/or tablet formulations) with any other antifungal medications with activity against aspergillosis, medications used in as combination therapy should be recorded.

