7.2.5.5 Patient Index Date and Specific Treatment Assessment Durations

Patient index date is defined as the date of the first treatment of posaconazole injection and/or tablet formulations.

	30
PRODUCT: MK5592	PROTOCOL/AMENDMENT VERSION NO.: 2
REVOPS ID NO: NIS102646	CORE DRC APPROVAL DATE: 18-SEP-2024
EPIDEMIOLOGY NO.(PE STUDIES ONLY): EP08047.004	

Specific treatment assessment duration for different outcomes are summarized as follows:

- Assessment for all-cause mortality for IA will occur at Day 42. Treatment may continue beyond Day 42.
- Assessment for overall response will occur at the end of treatment (for both first line and salvage treatment). Patients may continue treatment beyond 12 weeks (84 days) however assessment for response to therapy will occur at 84 days for such patients. For patients who receive less than 12 weeks of treatment, assessment will occur at the end of posaconazole treatment.

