7.3.2.1 Primary Outcomes

The primary outcome is all-cause death among proven, probable, possible IA patients who received at least 7 days of posaconazole injection and/or tablet formulations treatment through Day 42.

Death is defined as a patient with death is recorded in the medical history or death certificate can be provided through Day 42 or within Day 42. (Data cources see 7.4)

Patients with missing or 'unable to determine' dead or alive status through Day 42 will be excluded.

PRODUCT: MK5592	PROTOCOL/AMENDMENT VERSION NO.: 2
REVOPS ID NO: NIS102646	CORE DRC APPROVAL DATE: 18-SEP-2024
EPIDEMIOLOGY NO.(PE STUDIES ONLY): EP08047.004	

Secondary Outcomes 7.3.2.2

7.3.2.2.1 **Clinical response**

The clinical response of proven, probable, possible IA patients who received posaconazole injection and/or tablet formulations treatment as the first line or salvage treatment at the end of posaconazole treatment.

Clinical responses will be defined by using the 2017 Chinese guidelines for the diagnosis and treatment of invasive fungal disease in patients with hematological disorders and cancers (the fifth version) (Table 1) or by the investigator⁷(s).

⁷Considering the low compliance with guidelines in real-world clinical practice, it is possible that there may be insufficient information from medical record to support the definition of clinical response according to the guideline (Table 1). Therefore, investigator's professional judgment could be used to define the clinical response. The subgroup analysis by the methods of clinical response definition (guideline vs. investigator's professional judgment) will be conducted depending on data availability. (see 7.7.2.1)

See Table 1 for the definitions for clinical response from the 2017 Chinese guidelines for the diagnosis and treatment of invasive fungal disease in patients with hematological disorders and cancers (the fifth version). The Chinese guidelines are consistent with the 2008 EORTC/MSG guidelines.

Table 1 Clinical Response Definitions from the 2017 Chinese guidelines for the diagisnos and treatment of invasive fungal disease in patients with hematological disorders and cancers (the fifth version).

Outcome, Response	Criteria
Success	

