7.8 Data Analysis

A descriptive analysis of the distribution of values abstracted for each variable will be provided. For the continuous variables we are interested, the values of mean/median, standard deviation (SD), min/max, interquartile range (IQR, including the first quartile [Q1] and third quartile [Q3]) will be calculated; the frequency and percentages will be calculated for these categorical variables. All analyses will be carried out using all available data. A participant with missing data on one variable will be used only in calculations that do not involve that variable.

	39
PRODUCT: MK5592	PROTOCOL/AMENDMENT VERSION NO.: 2
REVOPS ID NO: NIS102646	CORE DRC APPROVAL DATE: 18-SEP-2024
EPIDEMIOLOGY NO.(PE STUDIES ONLY): EP08047.004	

All analyses will use SAS (SAS Institute Inc., Cary, North Carolina). Detailed statistical analysis plan (SAP) and corresponding mock-up tables/figures/listings will be described separately prior to the commencement of any analyses.

All analysis detailed will be described in a separate "Statistical Analysis Plan". Key points are listed below.

7.8.1 **Primary Objective**

The primary objective is to assess the all-cause mortality of using posaconazole for proven, probable, possible IA patients. The all-cause mortality will be calculated with 95% CI.

Total all-cause mortality=number of total IA patients who die through Day 42/number of all IA patients (proven, probable, possible) included in the study with dead or alive status reported x 100%.

All-cause mortality by treatment line=number of IA patients by treatment line who die through Day 42/number of IA patients by treatment line (proven, probable, possible) included in the study with dead or alive status reported x 100%.

The analysis will be stratified by method of data collection: prospective vs. retrospective.

The following subgroupanalysis may be conducted depending on data availability:

- 1. Treatment duration (e.g. group by median treatment duration, etc);
- 2. Patients who only receive Posaconazole injection vs patients who receive Posaconazole injection then Posaconazole tablet;
- 3. Risk factors for mortality and poor outcome (Allogeneic hematopoietic stem cell transplant (HSCT); Relapsed leukemia, undergoing salvage chemotherapy; Liver transplant recipients)
- 4. IA at sites: Pulmonary IA vs others (sinus/upper respiratory involvement or disseminated disease to other organs).

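### Section 7.1 caps the primary mortality set at 42 days of treatment, against every other definition in the protocol; applied literally, it would bias Day-42 mortality upward

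*Protocol*

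**What the plan says.** Section 7.1 lists three evaluable sets that apply once eligibility has been checked. Item (1), for the primary objective, is "The patients who have continued posaconazole treatment for 7 to 42 days and have dead or alive status available through day 42". Item (2), for first-line response, begins "The patients who have continued posaconazole as first line treatment for 42 to 84 days". Item (3), for salvage response, covers 7 to 84 days.

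Elsewhere the primary population has a lower bound only:

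- Section 6.1 places the primary objective "in Chinese adult patients who receive at least 7 days" of posaconazole. Footnote 2 adds an 80% adherence allowance.
- Section 7.2.1 defines the study population as those "who received at least 7 days of posaconazole (injection and/or tablet formulations) treatment".
- Section 7.3.2.1 repeats the 7-day minimum and names one exclusion: "Patients with missing or 'unable to determine' dead or alive status through Day 42 will be excluded".
- Section 7.8.1 gives the denominator of total mortality as "number of all IA patients (proven, probable, possible) included in the study with dead or alive status reported".
- Section 7.2.5.5, in the bullet on mortality assessment, says "Treatment may continue beyond Day 42".

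The time origin is also in section 7.2.5.5: "Patient index date is defined as the date of the first treatment of posaconazole injection and/or tablet formulations". Section 7.5 expects 55-70 cases in all, of which 30-40 serve the primary objective.

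**The concern.** Item (1) contains two separate conditions: a range of treatment duration and availability of vital status. The upper end of that range appears in no other definition of the primary population. Two analysts, one working from 7.1 and one from 7.8.1, could report different primary results from the same data.

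The difference would not be neutral. Whether a patient is treated beyond Day 42 depends on surviving to Day 42, so an upper limit on duration selects on the outcome. Mortality is the only primary endpoint of an uncontrolled estimation study, and no comparator arm would share the distortion. The exact confidence interval would not reflect it either.

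**Working it through.** **1. The plan's own figure.** Table 2 in section 7.5 uses exact (Clopper-Pearson) intervals. All ten rows reproduce to 0.1 point. At 30% mortality, 9/30 gives (14.7, 49.4) with half-width 17.3, and 12/40 gives (16.6, 46.5) with half-width 15.0. The arithmetic of Table 2 is not in question.

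**2. The definitions side by side.**

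| Protocol section | Treatment duration | Vital status |
|---|---|---|
| 7.1 item (1) | 7 to 42 days | known through Day 42 |
| 6.1 | at least 7 days | not stated |
| 7.2.1 | at least 7 days | not stated |
| 7.3.2.1 | at least 7 days | missing or undeterminable excluded |
| 7.8.1 | no limit stated; all included patients | reported |
| 7.2.5.5 | may run past Day 42 | assessed at Day 42 |

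Read literally, a first-line patient can be in both item (1) and item (2) only with exactly 42 days of treatment.

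**3. Direction.** Among patients with at least 7 days of treatment and known status, let D be deaths through Day 42, S1 survivors who stopped by Day 42, and S2 survivors still treated after Day 42. Section 7.8.1 estimates p = D/(D + S1 + S2). Item (1), read literally, estimates D/(D + S1). A patient who dies by Day 42 cannot have been treated beyond it, so every death stays in and only S2 leaves. The second ratio cannot be below the first.

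**4. Size.** With f = S2/(S1 + S2), the literal set estimates

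p / (p + (1 − p)(1 − f)).

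The protocol does not give f, so the range below is assumed. The values of p span the 15%-50% assumed in section 7.5.

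| True p | f = 10% | f = 25% | f = 50% |
|---|---|---|---|
| 15% | 16.4% | 19.0% | 26.1% |
| 30% | 32.3% | 36.4% | 46.2% |
| 50% | 52.6% | 57.1% | 66.7% |

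For p = 30% and f = 50%: 0.30 / (0.30 + 0.70 × 0.50) = 0.30/0.65 = 46.2%. In counts, take the Table 2 row with 12 deaths among 40. There are 28 survivors, 14 of them are removed, and 12/26 = 46.2%.

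At p = 30% the bias is therefore +2.3, +6.4 or +16.2 points. The planned half-width is 17.3 points (N=30) or 15.0 points (N=40).

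**5. Consequence for section 7.5.** If all 55-70 enrolled patients had known status and entered the primary analysis, exact half-widths for mortality of 15%-50% would be about 10.2-13.8 points (N=55) or 9.0-12.2 points (N=70). The range stated in the plan is 12.1-18.7 points.

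**The case against.** The strongest reply is that 42 days in item (1) is an assessment point and not an exclusion. The protocol uses its 84-day limit that way: sections 7.2.5.5 and 7.3.2.2.1 keep patients treated beyond 84 days and assess them at Day 84. The sentence allowing treatment past Day 42 sits in the mortality bullet itself. An analyst who follows section 7.8.1 produces no bias. This reading is plausible and stands as a possibility. However, for the 84-day limit the protocol states what happens to longer-treated patients, and item (1) of 7.1 has no matching statement.

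A reader might infer more than the documents support in four respects:

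- *That the exclusion is certain, because 7.1 sorts patients into objectives by duration.* The three items are not a partition: salvage patients treated 7 to 42 days meet both (1) and (3).
- *That 30-40 of 55-70 proves a restricted primary set.* The primary objective was limited to first-line patients until the August 2024 amendment. The log entry for that change does not list section 7.5, and the entry that does list it concerns the timeline. The 30-40 may be a leftover first-line count.
- *That the error is 14 to 19 points.* That follows from assuming stopping times uniform over 7-84 days, which puts f at about 55%. It is one scenario, and nothing in the protocol fixes f. The first-line response objective requires at least 42 days of treatment, so f near zero is hard to sustain for first-line patients, but that gives no number.
- *That all survivors are removed.* Those removed are survivors, but survivors who stopped between Day 7 and Day 42 remain. There is also one small exception to the rule that only survivors leave: section 7.3.2.2.3 lets the stop date be the expected end of dispensed medication, so a patient who died could carry a recorded stop after Day 42.

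**Conclusion.** The contradiction is established: 7.1 item (1) states an upper limit on treatment duration that 6.1, 7.2.1, 7.3.2.1 and 7.8.1 do not have and that sits badly with 7.2.5.5. Whether it will be applied as an exclusion is not established.

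If it is applied, the bias in Day-42 mortality is upward by construction, apart from the recording exception on stop dates. Its size rests entirely on f. At a true 30% it runs from about 2 points (f = 10%) to about 16 points (f = 50%), the latter comparable to the planned half-width. If 42 days is only an assessment cap, the bias is nil and the fault is misleading wording. Either way the text has to be corrected, because it concerns the denominator of the only primary endpoint.

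**What to change.** Reword section 7.1 item (1) along these lines: all eligible patients who received at least 7 days of posaconazole (subject to footnote 2 of section 6.1) and whose dead or alive status is known through Day 42 from the index date are evaluated for the primary objective, whatever their total treatment duration. The vital-status condition should stay, because 7.1, 7.3.2.1 and 7.8.1 share it.

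Then reconcile section 7.5 and the abstract with that set. State whether 30-40 is still the expected primary number now that the objective covers both treatment lines and has no upper limit on duration, and recompute Table 2 if the number changes. Where the SAP defines the primary set, it should use the same definition.

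The cost is one reworded sentence plus a revised case count and, if needed, a revised table. No additional data are required.

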7.2 Setting

7.2.1 Study Population

The overall study population will consist of IA adult Chinese patients (proven, probable, possible⁵) who received at least 7 days of posaconazole (injection and/or tablet formulations) treatment (including monotherapy and combination⁶ therapy) from Mar 2022 to Dec 2024 (planned date of last patient in).

⁵ Follow the definition of 2020 EORTC/MSGERC or 2021 EORTC/MSGERC-ICU consensus criteria [Donnelly, J. P., et al 2020] (see Annex 5).

⁶Combination therapy is defined as patient use posaconazole (injection and/or tablet formulations) with any other antifungal medications with activity against aspergillosis, medications used in as combination therapy should be recorded.

7.2.2 Inclusion/Exclusion criteria for subjects receiving first line treatment

Inclusion criteria for subjects receiving first line treatment of IA:

- Chinese and resident in China;
- At least 18 years of age on the day of initiating posaconazole treatment;
- Diagnosed with proven, probable, possible IA per EORTC/MSGERC 2020 or 2021 EORTC/MSGERC-ICU criteria;
- Has received less than 7 days of other antifungal therapy with activity against aspergillosis (amphotericin, voriconazole, isavuconazole, or itraconazole) for treatment of the current episode of IA.

Exclusion criteria for subjects receiving first line treatment of IA:

- Unable to provide written informed consent if Ethics review committee (ERC) requires;
- Participating in any interventional clinical trial;
- Pregnancy or breast feeding during the treatment with posaconazole;
- Prior enrollment in current study (each subject may only be enrolled once);
- History or known aspergillus infection with a strain that is azole-resistance;
- Known or history of efficacy failure of posaconazole to treat a prior or current episode of IA.

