7.2.3 Inclusion/Exclusion criteria for subjects receiving salvage treatment

Inclusion criteria for subjects receiving salvage treatment of IA:

- Chinese and resident of China;
- At least 18 years of age on the day of initiating posaconazole treatment;
- Diagnosis of probable, proven, possible IA per EORTC/MSGERC 2020 or 2021 EORTC/MSGERC-ICU criteria;
- Has a diagnosis of IA with disease that is refractory to amphotericin B, voriconazole, itraconazole, isavuconazole or other antifungal medicines with activity against Aspergillus. Refractoriness is defined as progression of infection or failure to improveafter the receipt of 7 or more days of these medicinal products for treatment of the current episode of infection;

PRODUCT: MK5592	PROTOCOL/AMENDMENT VERSION NO.: 2
REVOPS ID NO: NIS102646	CORE DRC APPROVAL DATE: 18-SEP-2024
EPIDEMIOLOGY NO.(PE STUDIES ONLY): EP08047.004	

- OR
- Has a diagnosis of IA in patients who have shown intolerance to amphotericin B, voriconazole, itraconazole, isavuconazole or other antifungal medicines with activity against Aspergillus after the receipt of 1 or more days of any of these medicinal products given for the treatment of the current episode of infections.

Exclusion criteria for subjects receiving salvage treatment of IA

- Unable to provide written informed consent if ERC requires;
- Participating in any interventional clinical trial;
- Pregnancy or breast feeding during the treatment with posaconazole;
- Prior enrollment into the study (each subject may only be enrolled once);
- Known or history of efficacy failure of posaconazole to treat a prior or current episode of IA.

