7.2.5.2 The Recruitment Period

The recruitment period will start after the leading site contract signed (Oct 2023 as planned) and plan to be ended by Dec 2024.

During this period, inclusion/exclusion criteria checking by treatment line should be carried on for patients who are identified and observed during the patients identification period. Qualified patients after inclusion/exclusion criteria check should be recruited into the study and followed up.

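### First-line and salvage criteria overlap for patients intolerant after 1 to 6 days of a prior agent, and the protocol text states no precedence

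*Protocol*

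**What the plan says.** First line (Protocol 7.2.2) is defined by a day count: the patient "Has received less than 7 days of other antifungal therapy with activity against aspergillosis", with four agents named, for the current episode. Why the earlier agent was stopped plays no part.

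Salvage (Protocol 7.2.3) has two routes. The refractory route requires progression or no improvement after "the receipt of 7 or more days of these medicinal products for treatment of the current episode of infection". The intolerance route requires intolerance "after the receipt of 1 or more days of any of these medicinal products given for the treatment of the current episode of infections".

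Protocol 7.2.5.2 says that "inclusion/exclusion criteria checking by treatment line should be carried on for patients who are identified and observed", without saying what happens when both lists are met. Each list bars a second enrolment, which prevents double counting but does not assign a line.

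Line then governs the analysis. Protocol 7.8.1 gives total mortality and also "All-cause mortality by treatment line=number of IA patients by treatment line who die through Day 42" over the patients in that line. Protocol 7.8.2.1 gives the overall response rate by line only. Protocol 7.1 evaluates first-line response in "The patients who have continued posaconazole as first line treatment for 42 to 84 days", while salvage response is evaluated from 7 to 84 days.

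**The concern.** If a patient can properly be placed in either line, two sites can follow the protocol exactly and still report the same patient differently. The label changes more than the column in which the patient appears:

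- **Response rate.** A dual-eligible patient treated for 7 to 41 days counts if called salvage and is left out if called first line.
- **Mortality by line.** Numerator and denominator both move.
- **Eligibility.** Only the first-line list excludes azole-resistant strains, so for such a patient the label decides whether he or she enters the study.
- **Bias control.** Protocol 7.10 relies on reporting by line to separate patients by disease condition. That works only if line has one meaning.

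Retrospective data run from 29 March 2022 to the planned recruitment start in October 2023, and criteria are checked during recruitment. For most retrospective patients, Day 42 has therefore passed when the line is assigned. Assignment informed by outcome is possible, though inconsistent convention between sites is enough to cause the problem. The choice also arises at prospective enrolment.

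**Working it through.** **1. The plan's own figure.** Protocol 7.5, Table 2 uses exact binomial intervals: lower limit = Beta quantile 0.025 with parameters (x, n−x+1), upper limit = Beta quantile 0.975 with (x+1, n−x). For 6/40 this gives 5.7% to 29.8%, half-width 12.06, printed as 12.1. For 15/30 it gives 31.3% to 68.7%, half-width 18.70. All ten rows reproduce (4.5/30 by treating the count as continuous). The stated precision is not in question.

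**2. The overlap.** Let d be whole days of a named prior agent in the current episode, I intolerance and R refractoriness.

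- First line: d < 7.
- Salvage: (R and d ≥ 7) or (I and d ≥ 1).
- Both: I and 1 ≤ d ≤ 6.

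Enumerating d = 0 to 10 against I and R (yes/no) gives:

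| Days of prior agent | Meets both lists? |
|---|---|
| 0 | never |
| 1 to 6, intolerant | always |
| 1 to 6, not intolerant | never (first line only) |
| 7 or more | never |

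**3. Size for the response rate.** The protocol gives neither the split by line nor the number of dual-eligible patients, so these counts are assumed: 25 clear first-line patients (15 responders), 25 clear salvage patients (10 responders) and 6 dual-eligible patients (3 responders treated at least 42 days, 3 failures treated under 42 days). The total of 56 lies within the planned 55 to 70.

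| Uniform rule | First line | Salvage | Difference |
|---|---|---|---|
| All six to salvage | 15/25 = 60.0% | (10+3)/(25+6) = 13/31 = 41.9% | 18.1 points |
| All six to first line | (15+3)/(25+3) = 18/28 = 64.3% | 10/25 = 40.0% | 24.3 points |

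In the second row the three early failures fall outside the 42-day window and count nowhere. Without that window, first line would be 18/31 = 58.1%, so the rise to 64.3% comes from the window acting through the label.

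**4. Size for mortality by line.** Assumptions: 55 patients with known status, 5 dual-eligible, 25 clear patients per line with 8 deaths each. A line shows 8/25 = 32.0% without the five. With them it shows between 8/30 = 26.7% (none of the five dies) and 13/30 = 43.3% (all die). Protocol 7.5 expects only 30 to 40 cases for the primary objective, where each patient would weigh more.

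**5. Total mortality.** With x deaths among the five, the total is (8+8+x)/55 under either label; for x = 2 it is 18/55 = 32.7% both ways. It changes only if the first-line azole-resistance exclusion removes a patient whom salvage would admit.

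**The case against.** The best reply is that the protocol already points to an answer. Secondary objective 2 (Protocol 6.2) places intolerant patients in the salvage population, and first line has no intolerance route. One could say that the specific criterion prevails over the general day count. That is a reasonable reading, but 7.2.2 still admits these patients and nothing tells a site to apply the criteria in that order. The enrolment figure is not shown and the SAP is not at hand. Either might settle the label for analysis, but a SAP cannot settle who is eligible.

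Three further objections stand:

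- The study is descriptive, with no hypothesis test and no planned contrast between lines. In the illustration each rate moves by only 1.9 to 4.3 points under a uniform rule, against an exact 95% interval for 15/25 of 38.7% to 78.9%.
- The loss of early first-line failures comes from the 42-day minimum. It affects all first-line patients, and exclusive lists would not cure it.
- Line and treatment history are already planned variables (Protocol 7.3.2.2.2 and 7.3.2.2.3), and prior days and intolerance are facts that precede the index date. Line can therefore probably be re-derived.

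A reader might infer that the choice of label could open a gap of about 29 points. On the same counts that means 18/28 = 64.3% against 10/28 = 35.7%, with every dual-eligible responder sent to first line and every failure to salvage. Nothing in the protocol suggests such sorting, so it is not an expected effect.

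**Conclusion.** The overlap is certain from the criteria as written, and the text shown does not resolve it. It affects mortality by line, the response rate and, for azole-resistant strains, eligibility. A reader might infer that the main Day-42 result is compromised. The documents do not support that, because total mortality does not depend on the label apart from the azole-resistance route.

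The size is unknown. If there are no dual-eligible patients, no rate moves. On the assumed counts the two uniform rules give 60.0% v 41.9% or 64.3% v 40.0%, and mixed labelling could move the rates further. This should be fixed before the by-line rates are reported; it does not undermine the total mortality estimate.

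**What to change.** Reconcile Protocol 7.2.2 and 7.2.3 with one sentence that makes the lines mutually exclusive, based only on facts dated before the index date: days of prior therapy and the reason for stopping. The sponsor chooses the precedence; either direction removes the ambiguity.

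Apply the rule uniformly by re-deriving line for all patients, including those already enrolled, and make sure that both facts are on the case report form. Report mortality and response by line with the dual-eligible patients assigned the other way as a sensitivity analysis, and state how many there are.

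The cost is a re-check of the label for patients with 1 to 6 days of prior therapy, plus one additional set of by-line rates. It needs no extra patients.

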7.2.5.1 The Patients Identification Period

The patient identification period will be defined as the segment of time from date of posaconazole injection and tablet formulations has been approved by NMPA for the treatment of IA in adult patients (29 Mar 2022) until the planned last patients in date of the study. The whole identification period will last for about 32 months.

IA Patients who admitted to the selected hospitals and received at least 7 days of posaconazole (injection and/or tablet formulations) treatment (including monotherapy and combination^ therapy) during this period should be identified and observed. The procedures of how to identify eligible patients is presented in section 7.4.1.

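### Three exclusions checked during recruitment have no reference date, so patients can be removed for resistance, treatment failure or trial entry that arose after posaconazole started

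*Protocol*

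**What the plan says.** Two eligibility criteria in 7.2.2 are tied to treatment: "At least 18 years of age on the day of initiating posaconazole treatment" and "Pregnancy or breast feeding during the treatment with posaconazole". Section 7.2.3 repeats both.

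Three exclusions are not tied to any date:

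- "Participating in any interventional clinical trial" (7.2.2 and 7.2.3);
- "History or known aspergillus infection with a strain that is azole-resistance" (7.2.2 only);
- known or past failure of posaconazole in an earlier or the current episode of IA (7.2.2 and 7.2.3).

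On timing, 7.2.5.2 says that during the recruitment period "inclusion/exclusion criteria checking by treatment line should be carried on for patients who are identified and observed during the patients identification period". Recruitment is planned from Oct 2023 to Dec 2024, while 7.2.5.1 starts identification on 29 Mar 2022. Section 7.1 states that "all patients accepted posaconazole injection and/or tablet previously in the course of routine clinical practice". Section 7.2.5.5 defines an index date, the first posaconazole treatment, but none of the three exclusions refers to it.

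**The concern.** Eligibility for a cohort that starts on the index date should depend on what was known by then. Here it is settled later, and for most retrospective patients after the Day 42 outcome is known. An exclusion without a date can then take in events that belong to the outcome or depend on it.

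Two of the three lines concern resistance and treatment failure, both closely related to mortality and response. Removing patients on those grounds would tend to make posaconazole look better. The third, trial participation, can act the other way, because a patient who has died cannot be participating on the day of the check. At stake are the Day 42 mortality, overall and by line, and the overall response rate. The confidence interval does not cover this kind of error.

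**Working it through.** **Timing.** The protocol gives months, so assume 1 Oct 2023 and 31 Dec 2024 as the recruitment limits. From 29 Mar 2022 to 1 Oct 2023 is 551 days, about 18 months; to 31 Dec 2024 is 1,008 days. The earliest patients are therefore checked at least 551 − 42 = 509 days after Day 42. Patients who started shortly before recruitment opened, and prospective patients, may be checked before Day 42.

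**Reading each line at the check.**

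- *Azole resistance.* A resistant strain first reported on Day 20 is known at a later check, so a first-line patient is removed on post-index information.
- *Efficacy failure.* Failure of the study course is a failure in the current episode, so first-line and salvage patients can be removed on something close to the outcome. Because the index date is the first injection or tablet treatment, little room remains for a current-episode failure that precedes it, other than an earlier course such as another formulation.
- *Trial participation.* At the check date the present tense can apply only to a living patient. A retrospective survivor who joined a trial later is removed. A patient who was in a trial at treatment start and has since left it or died is kept.

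**The plan's own figures.** Table 2 (7.5) uses exact Clopper-Pearson intervals, and all ten rows reproduce to rounding. The extremes are 6/40, giving 5.7% to 29.8% (half-width 12.1), and 15/30, giving 31.3% to 68.7% (half-width 18.7). The table is correct, and this point does not depend on it.

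**Illustration.** N is the planned 30 to 40 for the primary objective, with mortality inside the planned 15% to 50%. The number wrongly removed, k, is not in the protocol; 1 to 4 is assumed. With d deaths:

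- k survivors removed: d/(N − k)
- k patients removed, all of whom died: (d − k)/(N − k)
- k patients removed, half of whom died: (d − k/2)/(N − k)

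| N, d (mortality) | k | Survivors removed | All died | Half died |
|---|---|---|---|---|
| 30, 9 (30.0%) | 1 | 31.0% | 27.6% | 29.3% |
| 30, 9 (30.0%) | 4 | 34.6% | 19.2% | 26.9% |
| 40, 12 (30.0%) | 1 | 30.8% | 28.2% | 29.5% |
| 40, 12 (30.0%) | 4 | 33.3% | 22.2% | 27.8% |
| 40, 6 (15.0%) | 4 | 16.7% | 5.6% | 11.1% |
| 30, 15 (50.0%) | 4 | 57.7% | 42.3% | 50.0% |

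For example, 9/(30 − 4) = 34.6% and (9 − 4)/(30 − 4) = 19.2%. The last row shows that removing resistant or failing patients lowers mortality only if they die more often than the rest.

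**Response rate.** Removing k patients who would have counted as non-responders changes r/n to r/(n − k), which is always an increase. This applies only to patients otherwise in the response analysis. Under 7.1, first-line patients need 42 to 84 days of treatment, so those who stop earlier are already outside it.

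**The case against.** The strongest objection is that the trial exclusion has a more natural reading. Section 7.1 limits the study to posaconazole given in routine practice, so participation probably means participation at the time of treatment. That is a fair reading, and on it the survivor-only effect disappears. What stands is that the wording also permits the check-date reading, so sites may differ.

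A reader might go further and infer any of the following, none of which the protocol supports:

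- *That the trial exclusion always removes Day 42 survivors.* A patient checked before Day 42 may be alive and still die by Day 42. The effect is clear only for cases whose Day 42 has passed.
- *That first line is favoured over salvage because only 7.2.2 lists resistance.* The efficacy-failure exclusion is in both lists and on the same reading removes failing salvage patients too. Mortality is also reported by line (7.8.1), and no test between lines is planned (7.5).
- *That the net bias has a known sign.* The effects oppose each other and their frequencies are not given.

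It is also fair that shifts of a few points lie inside the planned half-widths of 12.1 to 18.7, and that results are stratified by prospective and retrospective collection. Stratifying shows where an effect may lie but does not restore removed patients. Section 7.10 discusses survivor, non-response and missing-data bias, but not eligibility judged after the outcome. Finally, Figure 2 (7.4.1) could not be read here; a reference time stated there would answer part of this point.

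**Conclusion.** The point holds as a defect of wording and timing. Read as written, the resistance exclusion (first line) and the efficacy-failure exclusion (both lines) can remove patients for events found during the study course. This would tend to lower mortality and raise the response rate, assuming that such patients do worse. The trial exclusion can act in the opposite direction among retrospective cases, but only on the check-date reading.

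Size and net direction cannot be determined from the protocol, and the figures above rest on assumed counts. There is no numerical error in the plan. The correction is worth making because it is simple and the selection concerns the outcome itself.

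**What to change.** In 7.2.2 and 7.2.3, judge the three exclusions at the index date of 7.2.5.5, stating that this date is the start of the posaconazole course under study. Suggested wording:

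- *participating in an interventional clinical trial on the index date* (both lists); later enrolment is recorded and does not exclude;
- *azole-resistant Aspergillus strain documented on or before the index date* (7.2.2);
- *efficacy failure of a posaconazole course given before the index date* (both lists).

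State that patients whose resistance or failure is found after the index date stay in the mortality denominator, and in the response denominator where they meet its other conditions. Re-check patients already screened out under these lines.

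The trial exclusion should not be widened to any participation up to Day 42 or Day 84. Someone who dies on Day 10 cannot join a trial on Day 30, so that window would again remove only patients who lived long enough to join. Changing the resistance line alone would not be enough either, since the same patient could still be removed under the efficacy-failure line.

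The cost is three lines of wording and a small re-check of the screening log. Some patients with resistance or failure may return, and the result may look slightly less favourable.
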